Eligibility	
 • HIV-infected women \geq 14 years • Daily access to mobile phone and willing to receive SMS • Literacy not required if women have access to a partner/family member whom she would be comfortable to have read her the messages. • Expected continued residence in study area for the study duration • Willing to provide informed consent • Not enrolled in other studies

e) RANDOMIZATION PROCEDURES

Participants will be randomized to: 1) Simple unidirectional SMS messaging, 2) Interactive bidirectional SMS dialogue, and 3) Control, using 1:1:1 allocation. A computer-generated randomization list will be generated using random block sizes in STATA. The allocation codes will then be put in sequentially numbered sealed envelopes. Participants and study will be un-blinded to randomization arms.

f) DATA COLLECTION PROCEDURES

Women will be followed during pregnancy and for two years postpartum; all clinical care will be managed through the existing MCH and CCC infrastructure. Because the study aims to determine mHealth benefits in a routine clinic setting, specific ANC/PMTCT/HIV services will be delivered by the MOH programs with minimal clinic interactions with study personnel. The study team will abstract data regarding clinic attendance, pill refills, infant health and infant HIV status from the PMTCT program registry, labor and delivery ward, pharmacy and peer counselors registers. Viral load and infant HIV testing results will be abstracted from the national electronic viral load dashboard. We will make check-in calls to all participants regardless of study arm at 1 month and 1 year post-EDD. This will be done to ascertain mother's delivery status, infant status, and that phone number is up to date. Check-in calls will be done by data management teams and will call the participants contacts if they fail to reach study participant.

The study visit schedule will be: enrollment (any time in pregnancy), 6 weeks postpartum, then every 6 months up to 24 months. At each visit a standardized questionnaire will be administered using a tablet-based system (Open Data Kit, ODK) developed by the UW Department of

[figure not shown]

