**Table 2.1 Summary of primary and secondary endpoints**

Primary Endpoints	Indicator	Source
Maternal virologic non-suppression	HIV RNA $\geq 1000$ copies/mL	Maternal study visits at 6 wk, 6, 12, 18, 24 mo, and record abstraction for routine VL.
Retention	Seen within 2 weeks of scheduled visits	Record abstraction for scheduled clinic visits throughout study.
Loss to follow-up	Not seen in clinic for $\geq 6$ months	
Infant HIV-free survival	HIV DNA and antibody results, and mortality	Record abstraction, infant study visits, verbal autopsy.
Secondary Endpoints	Indicator	Source
Drug Adherence	Pharmacy: % days covered since last refill Self-report: % doses taken in last 30 days *pharmacy data viewed as primary analysis of secondary endpoint	Pharmacy: record abstraction throughout study Self-report: questionnaire at study visits
Maternal drug resistance	OLA	Resistance assay in mothers with virologic failure

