#### Primary

1. **Viral non-suppression (virus detected at  $\geq 1000$  copies/mL):** Generalized estimating equations (GEE) with log-binomial link will be used to compare the 2-way or 1-way arms versus control arm for prevalence of viral non-suppression at any time during follow-up. All available data will be used after enrollment and  $\geq 4$  months since ART start, but any observed unsuppressed VL within 30 days after an unsuppressed VL will be excluded. As secondary analyses, Andersen-Gill analysis will be used to compare incidence of viral non-suppression in the 2-way or 1-way arms versus control arm at any time during follow-up. The proportions of women ever experiencing viral non-suppression as well as the cumulative incidence by delivery, 180 days postpartum, 365 days postpartum, and 730 days postpartum will be compared between arms by log-binomial regression.
2. **Retention in care.** GEE with log-binomial link will be used to compare arms for proportion of visits attended within 2 weeks of scheduling throughout study follow-up. The proportions of women lost to follow-up by 12 and 24 months postpartum will be compared between study arms by log-binomial regression.
3. **Infant HIV-free survival.** Incidence of infant HIV acquisition or death will be compared between study arms using Cox proportional hazards regression.

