**Table 5.2 Study endpoints: shell table**

	Overall	Control	One-way	Two-way	p-value (one-way vs. control)	p-value (two-way vs. control)	p-value (either intervention vs. control)	p-value (one- way vs two- way)+
MATERNAL OPTION B+								
Virologic non-suppression ever (VL $\geq$ 1000 copies/mL) (n, %)								
Prevalence of virologic non-suppression **								
Incidence of virologic non-suppression (per 100 py)								
*With virologic non-suppression by delivery (%)								
*With virologic non-suppression by 180 days postpartum (%)								
*With virologic non-suppression by 365 days postpartum (%)								
*With virologic non-suppression by 850 days postpartum (%)								
Retention								
Scheduled clinic visits attended on time since enrollment per participant (%)								
To 12 months postpartum								
To 24 months postpartum								
*Loss to follow-up (%)								
By 12 months postpartum								
By 24 months postpartum								
^Infant HIV and mortality								
Infant HIV incidence (per 100 py)								
Infant mortality (per 1000 live births)								
Infant HIV-free survival (per 100 py)								

Drug resistance (DR) ^Cumulative incidence of DR per 100 py *DR at 6 months postpartum (%) *DR at 12 months postpartum (%) *DR at 24 months postpartum (%)**							
---	--	--	--	--	--	--	--

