**Adherence**

\$Self-reported adherence <95% over entire

follow-up (%)

\$Refill-based adherence <95% over entire

follow-up(%)

\$ Compared by GEE Log-binomial regression

& Compared by Andersen-Gill regression

^ Compared by Cox proportional hazards regression

\* Compared by Log-binomial regression

+ Exploratory comparison

\*\* All available VL after enrollment and  $\geq 4$  months after ART start will be included

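### The formal comparison of viral non-suppression by delivery has no scheduled post-enrolment viral load in its window, so it depends heavily on unscheduled routine testing

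*SAP*

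**What the plan says.** SAP section 5.3 (Primary, item 1) makes a GEE comparison of prevalence the main analysis of viral non-suppression. Among the analyses listed after it, the "cumulative incidence by delivery, 180 days postpartum, 365 days postpartum, and 730 days postpartum will be compared between arms by log-binomial regression". Table 5.2 carries the first horizon as the row "With virologic non-suppression by delivery", starred for log-binomial regression. The table has four p-value columns, of which one-way versus two-way is marked exploratory.

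The data rule follows directly on the GEE sentence. It begins "All available data will be used after enrollment" and then requires at least 4 "months since ART start, but any observed unsuppressed VL within 30 days after an unsuppressed VL will be excluded". In Table 5.2 the rule reappears as a footnote starting "All available VL after enrollment and". That footnote is attached to the prevalence row and to one drug-resistance row, not to the delivery row.

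The visit schedule in the Protocol (Phase 2, Data collection procedures) is "enrollment (any time in pregnancy), 6 weeks postpartum, then every 6 months up to 24 months". SAP Table 2.1 gives the source of the endpoint as "Maternal study visits at 6 wk, 6, 12, 18, 24 mo, and record abstraction for routine VL". Protocol Table 8 lists only the postpartum visits. Blood for viral load is drawn at every study visit, so an enrolment value exists. SAP Table 5.1 reports it as a baseline characteristic, split at 4 months of ART.

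The Protocol's eligibility text (Phase 2, Recruitment procedures) admits ARV-naive, previously treated and currently treated women up to about 36 weeks' gestation. Neither document gives the denominator of the delivery row, or the interval or coverage of routine antenatal viral load testing.

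**The concern.** A cumulative proportion by a given time can be compared between arms only if the arms are measured alike up to that time. Between enrolment and delivery the trial measures nobody on schedule. What enters the row is whatever the clinics happened to test, and that depends on attendance.

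Attendance is what the intervention aims to change. The SMS arms receive visit reminders and missed-visit messages, and better retention is part of the trial's first hypothesis. If SMS brings more women to antenatal visits, more of them may be tested and more non-suppression may be found. The row could then count against SMS with no true difference, or hide a true benefit. Readers are likely to take this horizon as evidence on the antenatal period, and the plan would print p-values beside it.

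**Working it through.** The plan gives no sample size, power or coverage for this row, so it has no figure of its own to reproduce. As a check on the formula used in step 5, the SAP's 75% v 85% case gives n = [1.96√(2×0.20×0.80) + 0.842√(0.25×0.75 + 0.15×0.85)]² / 0.10² = 250 per arm, which matches SAP section 3.

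**1. Scheduled viral loads in the window.** The study visits are enrolment, 6 weeks postpartum, then 6-monthly. The number after enrolment and before delivery is zero.

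**2. Effect of the 4-month rule.** 4 months = 4 × 365.25 / 12 / 7 = 17.4 weeks. The latest gestation at ART start that allows an eligible value before delivery is (gestation at delivery − 17.4):

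- delivery at 37 weeks: 19.6
- delivery at 40 weeks: 22.6
- delivery at 42 weeks: 24.6

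For delivery at 40 weeks, the eligible window is max(0, 40 − gestation at enrolment − 17.4) for a woman starting ART at enrolment. For a woman already on ART for more than 4 months it is 40 − gestation at enrolment.

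| Gestation at enrolment (weeks) | Starting ART at enrolment | Established ART |
|---|---|---|
| 12 | 10.6 weeks | 28 weeks |
| 20 | 2.6 weeks | 20 weeks |
| 24 | 0 | 16 weeks |
| 36 | 0 | 4 weeks |

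**3. How many established-ART women might be tested (assumption).** Suppose routine tests are evenly spread, every 26 or every 52 weeks. The chance of a test in the window is then window/26 or window/52: 77% or 38% for enrolment at 20 weeks, 62% or 31% at 24, 46% or 23% at 28, and 31% or 15% at 32. The documents give no interval, so this shows only how wide the range is.

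**4. All randomised women as denominator.** Untested women then count as having no event, so the observed proportion is coverage × true non-suppression. The coverages and the 20% and 25% below are illustrations, and neither example has a true effect.

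- 20% in both arms, 40% v 50% tested: 0.40 × 0.20 = 8% v 0.50 × 0.20 = 10%, ratio 1.25.
- 25% in both arms, 30% v 40% tested: 7.5% v 10.0%, ratio 1.33.

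Equal coverage gives a ratio of 1.0.

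**5. Tested women only as denominator.** The first example becomes 20% v 20%, ratio 1.0, if tested women represent their arms equally well. The cost is size. Take 275 less 10% = 248 per arm and the SAP's planning difference of 25% v 15% non-suppression. Power = Φ{[0.10√n − 1.96√(2×0.20×0.80)] / √(0.25×0.75 + 0.15×0.85)} is 80% at full coverage (n = 248), 50% at half coverage (n = 124) and 24% at one-fifth coverage (n ≈ 50).

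**6. If the rule does not cover this row.** The enrolment value is then the one scheduled measurement by delivery. It precedes the intervention, so viraemia at entry, including that of women just starting ART, is scored as an outcome. Randomisation balances it in expectation; it dilutes any effect and does not favour an arm.

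**The case against.** The strongest reply has four parts.

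- **Scope of the rule.** The rule's footnote is not attached to this row, so a scheduled value (enrolment) may fall in the window. The text does leave this open. It does not rescue the row, because step 6 then applies.
- **The 4-month exclusion.** For women who started ART by enrolment, eligibility depends on ART start date and gestation, both fixed before randomisation. The exclusion alone therefore costs information and does not bias the arms. This stands. Not counting viraemia before ART has had time to act is also a sensible definition.
- **Weight.** This is one horizon of a secondary analysis, and the primary GEE comparison uses repeated observed values without it. This stands too.
- **Replacement.** A 6-week comparison also depends on attendance, and with the 4-month rule kept it still excludes late ART starters. This is true, but that visit is scheduled in every arm and the eligible group is wider.

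A reader might infer that the row mainly measures who received a routine antenatal test, or that most women would be untested. The documents do not support either. Both need coverage figures, and the first also needs an all-randomised denominator; neither document supplies these. Women on established ART can contribute, their share is not stated, and step 3 allows coverage above one half under 6-monthly testing. Nor is a rise in testing from SMS shown; it is a plausible consequence of the trial's own hypothesis.

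**Conclusion.** The concern holds as a defect in one secondary comparison. On the natural reading of SAP section 5.3, the row rests only on unscheduled routine values and excludes ART starts after about 22.6 weeks' gestation (delivery at 40 weeks). On the other reading it counts baseline viraemia as an outcome. Neither reading supports a formal test of an SMS effect before delivery.

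The timing result rests on the documents plus the assumed gestation at delivery. The size of any distortion cannot be fixed from the documents: ratios of 1.25 to 1.33 with no true effect arise under the assumed coverages and an all-randomised denominator, and disappear with a tested-only denominator, which leaves a smaller, selected group. The primary conclusion is unaffected. The change is still worth making, because as written the plan produces between-arm p-values on a horizon without a scheduled post-enrolment measurement.

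**What to change.** In SAP section 5.3 and Table 5.2:

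- Make the delivery row descriptive, without p-values: by arm, the number of women with an eligible antenatal viral load and the number at or above 1000 copies/mL, with the enrolment value excluded.
- State whether the data rule (after enrolment, at least 4 months after ART start) governs all the cumulative rows.
- Place the first formal comparison at the scheduled 6-week postpartum viral load, in a stated window, with the number tested shown by arm.
- State the at-risk set for that comparison. With the 4-month rule kept and delivery at 40 weeks, it is women who started ART by about 40 + 6 − 17.4 = 28.6 weeks' gestation.

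The cost is a few lines of SAP text and changes to the shell table. A formal antenatal comparison is lost, but the visit schedule could not support one. The 6-week comparison still depends on attendance, so the tested counts must be reported beside it.

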#### Secondary

1. **ART adherence.** ART adherence will be compared in the 3 study arms using GEE. ART adherence postpartum will be compared as a continuous variable between study arms by ANOVA at 6, 12 and 24 months postpartum.
2. **Drug resistance.** Incidence of drug resistance on ART will be compared between study arms using Cox proportional hazards regression. Proportion of women with resistance will be compared at 24 months between arms using Chi square tests.

**Table 5.2 Study endpoints: shell table**

	Overall	Control	One-way	Two-way	p-value (one-way vs. control)	p-value (two-way vs. control)	p-value (either intervention vs. control)	p-value (one- way vs two- way)+
MATERNAL OPTION B+								
Virologic non-suppression ever (VL $\geq$ 1000 copies/mL) (n, %)								
Prevalence of virologic non-suppression **								
Incidence of virologic non-suppression (per 100 py)								
*With virologic non-suppression by delivery (%)								
*With virologic non-suppression by 180 days postpartum (%)								
*With virologic non-suppression by 365 days postpartum (%)								
*With virologic non-suppression by 850 days postpartum (%)								
Retention								
Scheduled clinic visits attended on time since enrollment per participant (%)								
To 12 months postpartum								
To 24 months postpartum								
*Loss to follow-up (%)								
By 12 months postpartum								
By 24 months postpartum								
^Infant HIV and mortality								
Infant HIV incidence (per 100 py)								
Infant mortality (per 1000 live births)								
Infant HIV-free survival (per 100 py)								

Drug resistance (DR) ^Cumulative incidence of DR per 100 py *DR at 6 months postpartum (%) *DR at 12 months postpartum (%) *DR at 24 months postpartum (%)**							
---	--	--	--	--	--	--	--

**Adherence**

\$Self-reported adherence <95% over entire

follow-up (%)

\$Refill-based adherence <95% over entire

follow-up(%)

\$ Compared by GEE Log-binomial regression

& Compared by Andersen-Gill regression

^ Compared by Cox proportional hazards regression

\* Compared by Log-binomial regression

+ Exploratory comparison

\*\* All available VL after enrollment and  $\geq 4$  months after ART start will be included

## 5.4 INTERIM ANALYSIS

An interim analysis for maternal virologic suppression and failure and infant HIV-free survival will be performed using O'Brien-Fleming boundaries for benefit and futility when 50% of expected person time has been accrued.

## 5.5 MISSING OUTCOME DATA

While we will attempt to trace all study participants at 24 months postpartum, we anticipate that VL data may be incomplete due to participant loss to follow-up – either due to loss from care, or silent transfer to another facility. Due to the level of missingness we expect, we will not conduct any formal imputation. We will conduct sensitivity analyses for infant HIV-free survival assuming all infants who were lost to follow-up acquired HIV or died immediately after birth or survived HIV-free to 24-months postpartum.

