Computer Science and Engineering collaborators. Between study visits, data will be obtained from patient records in order to inform personalized, dynamic messaging. For example, if a participant in one of the intervention arms misses an appointment an appropriate SMS will be sent to address this absence and encourage the participant to reschedule. If a participant in the bidirectional arm does not respond after receiving two weekly messages, she will receive a check-in message asking if she is receiving messages. The study nurse will review clinical records daily to check for missed appointments, deliveries, clinic visits, infant immunizations, or any clinic contact from study participants. Delivery information from women will be obtained at 6 weeks postpartum and data abstracted from records at MCH-linked maternity centers. Follow-up will continue until 24 months postpartum.

In order to ensure completeness of clinic record abstraction for the study period, photographs will be taken at study exit of participants' CCC cards. All identifiable information, including name, date of birth, CCC number, ANC number and address will be covered with paper, and the record will be labeled with the participant's study ID only. Photographs will be transferred to a password-protected computer and secure server within 1 day of the photograph being taken and permanently deleted from the device used to capture the image. At the final study visit, in order to verify the data collected during abstraction, we will measure the height, weight, and mid-upper arm circumference of participants and their infants.

We will collect 14 ml maternal plasma samples for CD4 count, HIV viral load, and suspected drug resistance testing for mothers and 0.5 ml for HIV DNA DBS and HIV antibody testing for infants at all study visits. SOPs will be used to guide venipuncture procedure. The study will obtain viral loads for all participants. However, if the Kenyan MOH incorporates routine HIV viral load testing on a national scale and the testing intervals are similar to those proposed by the study, we will utilize viral load results from the standard of care rather than repeat viral loads.

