While retention procedures will be minimized in order to avoid contamination of the intervention on retention outcomes, we will obtain phone numbers of contacts and conduct home visits after enrollment to ascertain locator information. This information will be used at the end of the RCT to conduct home visits to re-establish contact for participants who failed to return for appointments and are lost to follow up in order to ascertain 24-month postpartum outcomes. Participants who are not able to attend the 24-month visit at the clinic will have their 24-month visit procedures conducted at the home visit. Figure 6 illustrates study flow from enrollment to follow up.

In addition to collecting data from study participants during the trial, a facility survey will be conducted with a facility manager at each study site to collect information regarding facility characteristics, Option B+ implementation, human resources, service disruption and service management. The purpose is to identify whether facility-level factors associated with participant clinical outcomes. No human-subject data will be collected.

Figure 6: Consolidated Standards of Reporting Trials-CONSORT diagram of RCT design

We will collect patient information at baseline and follow-up visits using:

- Participant surveys: demographics, clinical and sexual history, family planning, disclosure, medication adherence, experience with SMS and technology, intimate partner violence, and depression
- Medical and pharmacy record extraction forms will be completed by data teams: delivery information, infant immunizations, maternal health, infant health, medication adherence, lab forms, pharmacy data, maternal mortality, and infant mortality.

- Viral load and infant HIV test results will be abstracted from the national electronic VL dashboard.

g) VARIABLES: Outcomes, indicators, and source documents

Table 8: RCT Outcomes

Primary Outcomes	Indicator	Source
Retention	Seen at scheduled visits	PMTCT register for scheduled visits
Drug Adherence	Number/ expected	Self-report, pharmacy 6 wk, 6, 12, 18, 24 mos
Maternal viral suppression	HIV RNA	Maternal blood at 6 wk, 6, 12, 18, 24 mos
Maternal drug resistance	OLA	Resistance assay in mothers with viral failure
Infant HIV	HIV testing: DNA on DBS and antibody	HEI register week 6, infant specimens
Infant HIV-free survival	HIV DNA, antibody and mortality	HEI register week 6, Infant specimens 6, 12, 18, 24 mos; verbal autopsy

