## 2. STUDY ENDPOINTS

Primary study endpoints:

1. **Virologic non-suppression** will be defined for the primary endpoint using plasma viral load cut-off HIV RNA  $\geq 1000$  copies/mL for primary endpoint based on sample detection limits. A secondary cutoff at assay limit of detection (20c/ml for plasma and 839c/ml for DBS) will also be assessed.
2. **Retention in care** will be assessed based on medical record review of clinic attendance for scheduled clinical visits. Retention will be defined per participant as the proportion of scheduled visits to date attended within 2 weeks of their scheduled time and will be evaluated at 12 and 24 months postpartum. Loss to follow-up will be defined as no clinical visits for at least 6 months and will be evaluated at 12 and 24 months postpartum. Initial analyses will examine the 0-365 day interval and the 0-730 day interval.
3. **Infant HIV-free survival** will be assessed using infant HIV test and infant mortality data.

Secondary endpoints:

1. **ART adherence** will be assessed based on pharmacy refill data. For each refill period throughout the study, the proportion of days covered will be based on timing of refill collection. Self-reported adherence will also be assessed at study visits using a standardized questionnaire of the number of pills missed in the last 30 days and calculating percent adherence based on the expected number of doses taken. Self-reported adherence will be compared in secondary analyses.
2. **Drug resistance** will be assessed as detection of drug resistance mutations from plasma of women with HIV RNA  $\geq 1000$  copies/mL using the Oligonucleotide Ligation Assay (OLA).

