#### b. Analyses based on survival analysis

Assuming alpha=5%, power=80%, 2-sided test, 1:1:1 allocation ratio, with a sample size of 275 per arm, and 10% attrition, we will have sufficient power to

detect a Hazard Ratio (HR) of  $\leq 0.65$  in virologic failure, assuming an incidence rate of 25 per 100 person years (pys) in the control arm; a HR of  $\leq 0.55$  in drug resistance, assuming an incidence rate of 15 per 100 pys in the control arm; a HR of  $\leq 0.65$  in loss-to-follow-up, assuming an incidence rate of 25 per 100 pys in the control arm; and a HR of  $\leq 0.50$  in infant HIV or mortality (inverse of HIV-free survival), assuming an incidence rate of 10 per 100 pys in the control arm.

*Sample size for unidirectional or bidirectional SMS vs. control or unidirectional vs. bidirectional; gray shading shows cells with sufficient power and n is number per arm*

HR	Incidence in control			
	10%	15%	20%	25%
0.65	593	396	297	238
0.60	435	290	218	175
0.55	327	218	164	131
0.50	251	167	126	101

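### The two infant sensitivity scenarios treat every arm alike, so they never test whether lost infants fare differently by arm; the at-birth event date also overrides documented HIV-free results

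*SAP*

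**What the plan says.** Infant HIV-free survival is one of the primary endpoints in SAP section 2. Section 5.3 gives its analysis: "Incidence of infant HIV acquisition or death will be compared between study arms using Cox proportional hazards regression".

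Section 5.5 deals with missing outcomes. It rules out imputation ("Due to the level of missingness we expect, we will not conduct any formal imputation") and then gives the infant endpoint two scenarios, "assuming all infants who were lost to follow-up acquired HIV or died immediately after birth or survived HIV-free to 24-months postpartum". It specifies no missing-data sensitivity analysis for any other endpoint.

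The only definition of loss is in section 2, under retention in care: "Loss to follow-up will be defined as no clinical visits for at least 6 months and will be evaluated at 12 and 24 months postpartum". Infant loss has no definition of its own. The protocol (Phase 2, data collection procedures) provides for "HIV DNA DBS and HIV antibody testing for infants at all study visits", which fall at 6 weeks and then every 6 months to 24 months. For HIV-free survival, protocol Table 8 lists the week-6 register and "Infant specimens 6, 12, 18, 24 mos; verbal autopsy".

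**The concern.** There are two issues, and the second matters more.

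1. **Event date.** Loss is defined by a gap in attendance, so it can follow one or more negative results. An infant who was HIV-negative at 6 months and then lost cannot have been infected or have died immediately after birth. Taken literally, the first scenario still puts the event there and discards observed event-free time. SAP Table 5.2 reports infant HIV incidence and HIV-free survival per 100 person-years, so that scenario's rates and survival curves would be wrong even as an extreme case.

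2. **Same assumption in every arm.** Both scenarios move lost infants in the same direction in all arms. The missing question is whether infants lost despite SMS have different outcomes from infants lost without it. The question is live here: the trial is unblinded, retention is itself a primary outcome, and SMS is expected to improve it, so the mothers who are lost may differ between arms. Two scenarios that agree could be reported as evidence of robustness without that question having been examined.

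**Working it through.** **The plan's own figure.** SAP section 3b starts from "Assuming alpha=5%, power=80%, 2-sided test, 1:1:1 allocation ratio, with a sample size of 275 per arm, and 10% attrition" and takes a hazard ratio of 0.50 against a control rate of 10 per 100 person-years; its table gives 251 per arm.

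- Events (Schoenfeld): 4 × (1.960 + 0.842)² / (ln 0.50)² = 65.3, so 66.
- Exponential loss reaching 10% at 2 years has rate −ln(0.90)/2 = 0.0527 per year.
- Two-year event probability, λ/(λ + 0.0527) × [1 − exp(−2(λ + 0.0527))]: 0.172 for λ = 0.10 and 0.090 for λ = 0.05; mean 0.131.
- 66 / (2 × 0.1314) = 251 per arm. Reproduced.

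This figure is not in dispute; it fixes the inputs.

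**Planned scenarios against crossed scenarios.** Inputs: 275 per arm; HIV-free survival of 85% control and 95% intervention (SAP section 3a), so events in 15% and 5%. Assumption: equal loss in both arms, with those proportions applying to infants who are followed. RR is intervention events over control events, each out of 275.

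At 10% loss, 28 are lost and 247 followed per arm, with 37 control and 12 intervention events.

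| Assumption for lost infants | Intervention | Control | RR (95% CI) |
|---|---|---|---|
| All have the event (planned) | 12 + 28 = 40 | 37 + 28 = 65 | 0.62 (0.43–0.88) |
| All HIV-free (planned) | 12 | 37 | 0.32 (0.17–0.61) |
| Event in intervention only (crossed) | 40 | 37 | 1.08 (0.71–1.64) |
| Event in control only (crossed) | 12 | 65 | 0.18 (0.10–0.33) |

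At higher loss:

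| Loss per arm | Observed events (control, intervention) | Planned range | Crossed range |
|---|---|---|---|
| 20% (55 lost) | 33, 11 | 11/33 = 0.33 to 66/88 = 0.75 | 11/88 = 0.125 to 66/33 = 2.00 |
| 25% (69 lost) | 31, 10 | 10/31 = 0.32 to 79/100 = 0.79 | 10/100 = 0.10 to 79/31 = 2.55 |

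**How extreme the crossed case is.** At 10% loss the RR reaches 1 when 12 + x = 37. That means 25 of the 28 lost intervention infants (89%) have the event and none of the 28 lost control infants does.

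**Unequal loss with no true effect.** As an illustration, borrow the retention contrast in SAP section 3a (75% against 85%) as infant loss of 25% control and 15% intervention, with 15% events in both arms. Lost: 69 and 41. Observed events: 31 and 35. All-event scenario: (35 + 41)/(31 + 69) = 76/100, RR 0.76 (95% CI 0.59–0.97). All-free scenario: 35/31, RR 1.13 (0.72–1.78). The first shows an apparent benefit that comes only from fewer infants being lost.

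**Event date on the Cox scale.** Simulated Cox comparison: 200,000 per arm, control rate 10 per 100 person-years, true hazard ratio 0.50, visits at 6 weeks and 6, 12, 18 and 24 months, loss times uniform over 2 years (assumption).

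| Loss per arm | All-event, at birth | All-event, after last HIV-free visit | All HIV-free | Crossed extremes |
|---|---|---|---|---|
| 10% | 0.69 | 0.68 | 0.51 | 0.31 and 1.10 |
| 25% | 0.82 | 0.80 | 0.50 | 0.18 and 2.22 |

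In this set-up about 94% of lost infants have at least one earlier HIV-free visit, and dating the event at birth discards a mean of about 0.75 observed HIV-free years per lost infant. The hazard ratio changes by only 0.01 to 0.02.

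**The case against.** Several counter-arguments are sound and limit the point.

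- A reader might infer that dating the event at birth biases the treatment comparison. It hardly does, as the simulation shows. The damage is to person-time, rates and curves within that one scenario.
- The conflict with observed data depends on an undefined term. If infant loss meant only infants with no result after birth, the conflict would vanish. Nothing in the SAP says so, and the only definition given allows earlier visits. The same-assumption issue stands on either reading.
- A reader might infer that the SAP offers its pair as bounds on the effect. It does not; it calls them sensitivity analyses.
- A reader might infer that the planned scenarios ignore unequal loss. They do not: the all-event scenario moves the arms by different amounts when loss differs, as the 0.76 shows. What is absent is a different outcome among lost infants by arm.
- A reader might infer that a positive infant result would probably reverse. The documents give no evidence on outcomes among lost infants, and at 10% loss it takes 25 of 28 against none to bring the RR to 1.
- The protocol reduces loss through calls at 1 month and 1 year, national dashboard results, verbal autopsy and end-of-study home visits. It also says the trial is powered for maternal outcomes and only may have power for this endpoint. These measures lower the amount of missing data but do not tell the analyst how to treat what remains.

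**Conclusion.** The point stands as a gap in the sensitivity analysis of one primary endpoint. The consequential part is that no scenario lets outcomes among lost infants differ by arm. At the plan's event proportions and 10% loss, both planned scenarios give confidence intervals that exclude 1 (RR 0.32 and 0.62), while the crossed range of 0.18 to 1.08 includes 1. The gap between the two ranges widens with loss. In addition, the all-event scenario can show a benefit from unequal loss alone. The event date is a lesser defect: as written it conflicts with documented negative results, but it leaves the hazard ratio nearly unchanged.

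The sizes rest on assumed loss of 10% to 25%, on equal loss except in the one illustration, and, for the timing result, on loss spread evenly over 2 years. Whenever both arms lose infants, however, a shared assumption cannot produce the widest range. The primary Cox analysis is not in question.

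**What to change.** 1. Define infant loss to follow-up in SAP section 5.5.
2. In the adverse scenario, place the assumed event just after the infant's last documented HIV-free date, and at birth only for infants with no later result.
3. For each comparison in Table 5.2 (three between single arms, one pooling the SMS arms against control), add a tipping-point analysis that varies the event proportion among lost infants separately by arm, with the two crossed extremes as its end points. Report where the conclusion changes, so that readers can judge whether that combination is credible.
4. Report the number of lost infants by arm beside these results, so that an all-event estimate driven by unequal loss can be recognised.

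Cost: the crossed end points alone need eight further Cox fits (two for each of four comparisons), plus the grid between them. No new data are required. The sensitivity ranges to be reported will be wider.
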